7.1.1. Screening Phase and Pre-Treatment Assessments and Procedures

The Investigator, or designee, will identify a potential candidate for the EN3319-302 study. The Investigator, or designee, will obtain informed consent (and assent, according to the child's age as required by the Institutional Review Board [IRB]/Institutional Ethics Committee [IEC]) and will screen the subject at any time within 21 days of surgery. After the informed consent/assent has/have been signed, and a unique subject number has been assigned, Screening assessments/procedures will be completed (see [Table 3](#) and [Table 4](#)). Informed consent and assent from minors will be obtained prior to initiation of any study-related procedures. Blood samples for clinical laboratory tests may be collected at any time within 21 days prior to surgery. Clinical labs drawn as part of the SOC (including the pre-operative and intraoperative period) will be acceptable for study purposes provided they are taken prior to first surgical incision and assessed by the Investigator prior to the first dose of study drug. Details on selection of subjects will be based on their anticipated need for oral opioids for management of pain following surgery. The Investigator will explain the study to the subject (where age-appropriate) and to the subject's parent(s)/legal guardian(s). All Screening Phase assessments and procedures will be completed according to protocol preferably on the same day as outlined in [Table 3](#) (Single-Dose Phase) and [Table 4](#) (Multiple-Dose Phase). Each subject will also be assessed for his/her cognitive ability by the Investigator, or designee, to complete pain assessments and procedures as per protocol; documentation of the outcome will be recorded.

Screening visit activities will include:

- Obtaining written informed consent from parent(s)/legal guardian(s) and assent by minor (if required by the IRB/IEC)
- Recording demography: gender, age, and race
- Recording medical/surgical history: all previously existing and current medical conditions including any past surgical procedures. This assessment may be deferred until the preoperative or intraoperative time point.
- Performing physical examination: a comprehensive physical examination, including height and weight, to assess the subject's overall health and physical status. Record only abnormalities observed during the examination. This assessment may be deferred until the preoperative or intraoperative time point.
- Obtaining urine drug screen (see section [12.5.2](#)).
- Assessing entry criteria: inclusion/exclusion criteria will be assessed during the Screening Phase and confirmed prior to beginning Baseline assessments/procedures.
- Assessing cognitive ability of the subjects to complete pain assessments.
- Training subjects and parent(s)/legal guardian(s) on the proper use and completion of the pain assessments.
- Obtaining clinical laboratory tests: may be deferred until the preoperative or intraoperative time point provided the labs are drawn prior to the first surgical incision. Intraoperative drawn labs that are used for study evaluability must be assessed by the Investigator prior to administration of the first dose of study drug.

- Obtaining serum pregnancy test: female subjects of child-bearing potential will be given a pregnancy test.
- Measuring vital signs: temperature, heart rate (beats per minute), respiratory rate (breaths per minute), and blood pressure (systolic and diastolic blood pressure, mmHg).
- Collecting AEs/serious AEs (SAEs): all AEs/SAEs that occur during the Screening Phase and thereafter that started after Informed Consent/Assent, as applicable, has/have been signed.
- Completing a respiratory assessment: see section 12.2 for the tests to be included in this assessment.
- Completing a neurology assessment: see section 12.3 and Appendix A for the test to be included in this assessment.
- Recording prior and concomitant medications: medications taken within 30 days prior to signing consent/assent, as applicable, as well as ongoing medications. Note: Preoperative, intraoperative, and postoperative medications will be recorded (see Appendix B). Over-the-counter (OTC) acetaminophen or nonsteroidal anti-inflammatory drugs (NSAIDs) may be used only to manage fever or headache.

Blood samples for clinical laboratory tests must be collected at either the Screening Visit or during the preoperative or intraoperative period (prior to first surgical incision). Chemistry panels may include analysis of the analytes listed in section 12.5.3.

Hematology panels may include analysis of the analytes listed in section 12.5.4.

All appropriate restrictions on concomitant medication usage during the preoperative period should be followed per section 9.3.

7.1.2. Surgical Period (Preoperative or Intraoperative) Assessments and Procedures

Each subject will undergo surgery. Details of the surgical procedure(s) will be recorded on the appropriate source document and entered into the electronic case report form (eCRF) including the exact type of procedure(s) performed, the date and time of the surgery (start/stop time), and the time anesthesia/analgesia began and ended. The details of preoperative, intraoperative, and postoperative medications will be recorded (refer to Appendix B) .

Preoperative or intraoperative study procedures will include:

- Measuring vital signs: temperature, heart rate (beats per minute), respiratory rate (breaths per minute), and blood pressure (systolic and diastolic blood pressure, mmHg).
- Completing a respiratory assessment: see section 12.2 for the tests to be included in this assessment.
- Completing a neurological assessment: see section 12.3 and Appendix A for the test to be included in this assessment.
- Recording of surgical details

- Recording of food consumption: from 1 hour prior to administration of study drug; record all times that any food was consumed and what food was consumed (diet-as-tolerated [DAT], DAT-soft, full fluids [FFs], clear fluids [CFs], water).

If not already obtained at Screening, preoperative or intraoperative study procedures may include:

- Recording medical/surgical history
- Performing physical examination, including height and weight
- Obtaining clinical laboratory tests

Blood samples for clinical laboratory tests taken during the intraoperative period as part of the SOC may be used for study purposes provided they are collected prior to first surgical incision and assessed by the Investigator prior to the administration of the first dose of study drug.

- Chemistry panels may include analysis of the analytes listed in section 12.5.3.
- Hematology panels may include analysis of the analytes listed in section 12.5.4.

All appropriate restrictions on concomitant medication usage during the postoperative period should be followed per section 9.3.

7.1.3. Baseline Assessments and Procedures

Subjects who meet all inclusion/exclusion criteria will be enrolled into the study and assigned to receive a dose of oxymorphone HCl immediate-release oral liquid (study drug) based on order of enrollment.

Administration of the study drug will occur at the time postoperative parenteral analgesia is discontinued and oral dosing with opioid analgesics commences according to each institution's SOC. The subject's baseline level of pain will be assessed using an age-appropriate pain assessment instrument ([Appendix C](#), Faces Pain Scale-Revised [FPS-R]) or [Appendix D](#), the Face, Legs, Activity, Cry, Consolability scale [FLACC]).

The investigational staff will record the time, date, and dose of the study drug that the subject is administered in the source document and in the eCRF.

Baseline assessments and procedures will include the following:

- Assessing entry criteria: inclusion/exclusion criteria will be confirmed prior to beginning Baseline assessments/procedures.
- Retraining on completion of pain assessments: at Visit 2 before starting Baseline assessments and procedures.
- Obtaining urine pregnancy test: female subjects of child-bearing potential will be given a pregnancy test.
- Measuring vital signs: temperature, heart rate (beats per minute), respiratory rate (breaths per minute), and blood pressure (systolic and diastolic blood pressure, mmHg).

- Completing a respiratory assessment: see section 12.2 for the tests to be included in this assessment.
- Completing a neurological assessment: see section 12.3 and Appendix A for the test to be included in this assessment.
- Assessing current pain intensity (immediately prior to administration of study drug): each subject will provide a Baseline level of pain intensity using an age-appropriate pain assessment instrument (FPS-R for ages 6 to ≤ 12 ; FLACC for ages 2 to < 6 [see Appendix C and Appendix D, respectively]) prior to first dosing of study drug administration as well as just before each dose of study drug during the Multiple-Dose Phase; pain intensity scores will also be assessed just before taking the first rescue medication dose.
- Collecting a blood sample for pharmacokinetic assessment: draw prior to drug administration.
- Dosing the subject with study drug
 - The exact time when study drug was taken must be recorded. Any dose of study drug should not be administered for at least 2 hours following any opioid-based rescue medication.
 - For subjects receiving parenteral opioid analgesia: study drug will be administered when parenteral analgesia is discontinued and oral dosing with an opioid analgesic commences according to each institution's SOC.
 - Note: Laxative and antiemetic regimens may be used; all subjects will be allowed use of a laxative and antiemetic throughout the study. All study drug taken by the subjects (including rescue medication) will be recorded in the eCRF.
- Updating and recording all concomitant medications: medications taken within 30 days prior to signing consent/assent, as applicable, as well as ongoing medications. Note: Preoperative, intraoperative, and postoperative medications will be recorded (see Appendix B). OTC acetaminophen or NSAIDs may be used only to manage fever or headache.
- Collecting AEs/SAEs: all AEs/SAEs that occur during the Screening Phase and thereafter that started after Informed Consent/Assent, as applicable, has/have been signed.

7.1.4. Single-Dose Phase Assessments and Procedures

The following assessments and procedures will be performed during the Single-Dose Phase (see [Table 3](#)) after the baseline assessments have been completed and the subject is dosed. Every effort should be made to collect blood samples at the assigned time intervals relative to the time of administration of study drug:

- Assess and record current pain intensity at 15 and 30 minutes and at 1, 1.5, 2, 4, 6, 8, 12, and 24 hours (or upon ET) after administration of study drug or until the subject requires rescue medication. Assessments must be made by the Investigator, or designee. Pain will be assessed at time of rescue, but no pain assessments will be completed beyond administration of rescue medication.
- Measurement of vital signs at 15 and 30 minutes and at 1, 1.5, 2, 4, 6, 8, 12, and 24 hours (or upon ET) after administration of study drug.
- Assess respiratory (see section [12.2](#)) and neurological function (see section [12.3](#) and [Appendix A](#)) at 15 and 30 minutes and at 1, 1.5, 2, 4, 6, 8, 12, and 24 hours (or upon ET) after administration of study drug. Assessments must be made by the Investigator, or designee.
- Collection of blood samples for pharmacokinetic assessments at 15 and 30 minutes and at 1, 1.5, 2, 4, 6, 8, 12, and 24 hours (or upon ET) after administration of study drug.
- Record food consumption: capture the date and time of each consumption of food as well as what was consumed eg, DAT, DAT-soft, FFs, CFs, water from 1 hour prior to first dose of study drug administration through EOS/ET.
- Record rescue medication: provide rescue medication on an as needed basis for breakthrough pain (BTP). Rescue medication may include opioid-based patient controlled analgesia (PCA) rescue (but must NOT contain oxycodone or oxymorphone) for as long as the PCA device remains in place per SOC. Oral rescue medications will also be allowed during the study, but also must NOT contain oxycodone or oxymorphone.
- Monitor and document AEs/SAEs throughout the study.
- Update and record concomitant medications (including rescue medications).

Subjects will complete the Single-Dose Phase when they complete the EOS assessments and procedures at 24 hours (or upon ET) following initial study drug administration.

7.1.5. Multiple-Dose Phase Assessments and Procedures

The following assessments and procedures will be performed during the Multiple-Dose Phase (see [Table 4](#)) after the baseline assessments have been completed and the subject is dosed. Every effort should be made to collect blood samples at the assigned time intervals relative to the time of administration of study drug:

- Assess and record current pain intensity at 0.5, 1, 1.5, and 2 hrs post-Dose 1, and immediately prior to all remaining Doses administered up through 48 hrs after administration of the initial dose of study drug or until ET or the subject requires rescue medication. Assessments must be made by the Investigator, or designee. Pain will be assessed at time of rescue, but no pain assessments will be completed beyond administration of rescue medication.
- Measurement of vital signs at 0.5, 1, 1.5, and 2 hrs post-Dose 1, and immediately prior to all remaining Doses administered up through 48hrs (or upon ET) after initial administration of study drug.
- Assess respiratory (see section [12.2](#)) and neurological function (see section [12.3](#) and [Appendix A](#)) at 0.5, 1, 1.5, and 2 hrs post-Dose 1, and immediately prior to all remaining Doses administered up through 48hrs (or upon ET) after initial administration of study drug. Assessments must be made by the Investigator, or designee.
- Collection of blood samples for pharmacokinetic assessments at 0.5, 1, 1.5, and 2 hrs post-Dose 1, immediately prior to Doses 2, 3, 4, 5, 6, 7, and at 0.5, 1, 1.5, and 2 hrs post Dose 7..
- Record food consumption: capture the date and time of each consumption of food as well as what was consumed eg, DAT, DAT-soft, CFs, FFs, water from 1 hour prior to first dose of study drug administration through EOS/ET.
- Record rescue medication: provide rescue medication on an as needed basis for BTP. Rescue medication may include opioid-based PCA rescue (but must NOT contain oxycodone or oxymorphone) for as long as the PCA device remains in place per SOC. Oral rescue medications will also be allowed during the study, but also must NOT contain oxycodone or oxymorphone.
- Monitor and document AEs/SAEs throughout the study.
- Update and record concomitant medications (including rescue medications).

Subjects will complete the Multiple-Dose Phase when they complete the EOS assessments and procedures at 48 hours (or upon ET) following initial study drug administration.

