In the Multiple-Dose Phase, the first treatment cohort of 6 subjects from each age group will be given multiple doses of oxymorphone HCl immediate-release oral liquid at an initial dose recommended by the IDMC following postoperative parenteral analgesia according to each institution's SOC. The IDMC will use data from each age group's Single-Dose Phase to recommend the dose(s) to be used in each respective age group's Multiple-Dose Phase. Following completion of the first treatment cohort of 6 subjects within each group, the effectiveness, safety, and tolerability will be assessed by an external IDMC. Following their review, the IDMC may recommend that a second treatment cohort of 6 subjects in each group be dosed with oxymorphone HCl immediate-release oral liquid at the second dose (recommended by the IDMC). Following review of the effectiveness, safety, and tolerability of the second treatment cohort within each age group, the IDMC may recommend that a third treatment cohort of 6 subjects in each age group commence (at the third dose recommended by the IDMC; the IDMC may at this point recommend to end the Multiple-Dose Phase of the study).

If needed, non-oxycodone, non-oxymorphone rescue analgesia will be available according to the SOC at each institution.

Blood from a patent line will be collected to assess pharmacokinetics, examine dose proportionality, and estimate effective and safe dosing. An opioid antagonist (eg, naloxone based) will be readily available for immediate intravenous administration at the discretion of the Investigator; subjects requiring naloxone rescue will be discontinued from the study.

The study design for EN3319-302 is illustrated in [Figure 1](#).

Figure 1: Study Design for EN3319-302

FOOTNOTES:

- ^a Up to 3 ascending dose levels for the Multiple-Dose Phase will be selected from the results of the Single-Dose Phase by the IDMC
- ^b Each subject will only be enrolled into one of the treatment cohorts in either the Single-Dose Phase or the Multiple-Dose Phase; a subject will not progress from one treatment cohort to the next treatment cohort.
- ^c Dose will be selected based on IDMC recommendation and review of the results of the 0.10 mg/kg cohort (if a dose other than 0.15 mg/kg or 0.20 mg/kg is selected by the IDMC, the dose must not exceed 0.30 mg/kg); the IDMC may also recommend to proceed directly into the Multiple-Dose Phase

IR=Immediate Release; q4-6=Every 4 to 6 hours; SOC=Standard of Care

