NOTE: Within each age group, dose assignment will begin at lowest single dose and will proceed to the next dose after completion of all subjects. During the Single-Dose Phase, if rescue is needed, all study procedures (including PK) will continue except collection of pain scores. PK will only be discontinued if rescue is via oxycodone or oxymorphone. Within each age group, the Multiple-Dose Phase may proceed after IDMC assessment of the Single-Dose Phase data and selection by the IDMC of the treatment cohort doses that will be used in the Multiple-Dose Phase.

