7.1. Study Assessments and Procedures

A schedule of study assessments and procedures is provided in [Table 3](#) (Single-Dose Phase) and [Table 4](#) (Multiple-Dose Phase). The timepoints for the Single-Dose and Multiple-Dose Phase were designed to capture assessments/procedures/blood draws based on comprehensive blood sampling for pharmacokinetic analysis.

Subjects will be enrolled in either the 24-hour Single-Dose Phase or the 48-hour Multiple-Dose Phase, depending on the status of the study. Each subject will only be enrolled into one treatment cohort and will not progress from that treatment cohort into the next, higher dose level treatment cohort in this study. End-of-study (EOS) evaluations will commence immediately after completion of a subject's respective study phase (Single- or Multiple-Dose) or upon early discontinuation from the study; each subject will be required to complete all EOS evaluations and procedures unless consent/assent has/have been withdrawn. In this case, only adverse event (AE) information will be collected. A detailed account of the conduct of the study is provided after the schedule of study procedures.

Table 3: Schedule of Assessments/Procedures - Single-Dose Phase

Assessment	Visit 1		Visit 2 (Hospital)										Teleconference		
	Pre-Treatment		BL	After Dose (h)								EOS Evaluation (24h post 1st dose or ET)	Follow-Up (14d post EOS/ET)		
	Screening (within 21d of surgery)	(Pre-op or Intra-op) ^a		0.25	0.5	1	1.5	2	4	6	8	12			
Informed Consent by parent(s)/guardian(s)	X														
Assent by minor, if IRB-required	X														
Demographics	X														
Medical/Surgical History	X	or X													
Physical Examination	X	or X											X		
Assess Entry Criteria	X		X												
Train/retrain on completion of pain assessments ^b	X		X												
Assess cognitive ability to complete pain assessments ^c	X														
Urine Drug Screen	X														
Pregnancy test (serum/urine) ^d	X		X												
Study Drug Administration			X												
Blood sample for PK assessment			X ^e	X	X	X	X	X	X	X	X	X	X	X	
Vital signs	X	X	X	X	X	X	X	X	X	X	X	X	X	X	
Clinical laboratory tests ^f	X	or X											X		
Adverse Events/Serious Adverse Events ^g	X		Monitored Throughout Study ^h												
Respiratory assessment	X	X	X	X	X	X	X	X	X	X	X	X	X	X	
Neurology assessment	X	X	X	X	X	X	X	X	X	X	X	X	X	X	
Prior and Concomitant Medications ⁱ	X		Monitored Throughout Study ^h												
Pain Assessment (age appropriate) ^j			X	X	X	X	X	X	X	X	X	X	X	X	

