11. ASSESSMENT OF EFFECTIVENESS

11.1. Pain Intensity

Subjects in the 6 to ≤ 12 year old group (Group A) will receive training on completing the self-report pain assessments; completion of the training will be documented in the source record. Each subject (ages 6 to ≤ 12 years) will assess his/her pain intensity at the designated times during the study (see [Table 3](#) and [Table 4](#)) using the FPS-R. The Investigator, or designee will conduct the pain assessments at the designated times during the study (see [Table 3](#) and [Table 4](#)) for subjects in age group 2 to < 6 years (Group B) using the FLACC; all pain scores in age group B will be recorded by the Investigator, or designee.

Current pain intensity will be collected at the following times during the study:

- Single-Dose Phase: Immediately prior to dosing; 15 minutes, 30 minutes, 1, 1.5, 2, 4, 6, 8, 12, and 24 hours post dose (or upon ET) or just prior to administration of rescue medication. Upon rescue, any remaining scheduled pain assessments will be discontinued.
- Multiple-Dose Phase: Immediately prior to first dosing; 0.5, 1, 1.5, and 2 hrs post-Dose 1, and immediately prior to all remaining Doses administered up through 48hrs after administration of the initial dose of study drug or until ET or just prior to administration of rescue medication. Upon rescue, any remaining scheduled pain assessments will be discontinued.

Selection of pain scales in children is complex because there is no single instrument suitable for all ages. While the use of a visual analog scale (VAS) is commonly employed in adults for the assessment of pain, the use of a VAS in young children is complicated by communication barriers. The selection of data collection instruments in this study is based on those with the widest acceptability and best evidence of psychometric properties regarding the appropriateness in the target population. The Pediatric Initiative on Methods, Measurement and Pain Assessment in Clinical Trials (Ped-IMPACT) recommended core outcome domains (including pain intensity) to be considered in clinical trials for acute and recurrent/chronic pain, which included the FPS-R and the Numerical Rating Scale (PI-NRS).⁽¹⁵⁾

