12.4. Pharmacokinetic Assessments

12.4.1. Blood Sample Collections

Blood collection may be performed using an existing line (arterial or venous noted on eCRF) at the start of the study (the use of EMLA[®] at the insertion site is permitted). If access for blood sampling is lost, a new line will only be established as part of the clinical management of the subject; otherwise, the subject's participation in the study will be early terminated. Procedures for blood draws should follow institutional SOC. All catheter lines should be appropriately flushed per institutional SOC prior to each blood draws. The discard volume must be restricted to 0.5 mL for tubing with a dead space of ≤ 0.5 mL and up to 1.0 mL for tubing with a dead space > 0.5 mL. Calculation and evaluation of the following pharmacokinetic variables will be performed for all subjects participating in study: (Single-Dose Phase: C_{max} , T_{max} , AUC_{0-t} , AUC_{0-24} , $AUC_{0-\infty}$, λ_n , $t_{1/2}$, CL/F [clearance], and V/F [volume of distribution]; Multiple-Dose Phase: C_{max} , T_{max} , AUC_{0-t} , λ_n , $t_{1/2}$, and CL/F; see [Table 7](#) for definitions). Blood samples (0.5 mL) will be obtained and placed into 2.0-mL dipotassium ethylenediaminetetraacetic acid (K₂EDTA) tubes at each blood collection time point for both phases (see [Table 3](#) and [Table 4](#)). The samples will be obtained at the following times:

- Single-Dose Phase: Serial blood will be collected at time 0 (Baseline), at 15 and 30 minutes, and at 1, 1.5, 2, 4, 6, 8, 12, and 24 hours post dose.
- Multiple-Dose Phase: Serial blood will be collected at: 0 (Baseline), at 0.5, 1, 1.5, and 2 hrs post-Dose 1, immediately prior to Doses 2, 3, 4, 5, 6, 7, and at 0.5, 1, 1.5, and 2 hrs post Dose 7.

Table 7: Pharmacokinetic Variables

Variable	Definition
C_{\max}	Maximum plasma concentration; the highest concentration observed during a dosage interval
T_{\max}	The time at which C_{\max} was observed
AUC_{0-t}	Area under the concentration versus time curve from time 0 to the last measured concentration (C_t) in the dosing interval, calculated by linear trapezoidal rule
$AUC_{0-\infty}$	Area under the concentration versus time curve from time 0 to infinity, calculated as $AUC_{0-t} + C_t/\lambda_n$
AUC_{0-24}	Area under the concentration versus time curve from time 0 to 24 hours (end of dosing interval)

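### In the Multiple-Dose Phase, the four blood draws at 0.5 to 2 h after Dose 7 have no scheduled vital-sign, respiratory, sedation or pain reading beside them

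*Combined protocol and SAP*

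**What the plan says.** **Readings.** Section 7.1.5 sets "Measurement of vital signs at 0.5, 1, 1.5, and 2 hrs post-Dose 1, and immediately prior to all remaining Doses administered", and gives the same times for respiratory and neurological function and for pain. Section 11.1 repeats the pain times: after the Dose 1 series, readings come "and immediately prior to all remaining Doses administered up through 48hrs after administration of the initial dose". There is also a set of readings at end of study or early termination (section 7.1.6), and a pain score just before rescue. Oxygen saturation and heart rate are recorded when vital signs are taken (section 12.2), so they follow the same schedule. Section 12.6 refers back to the tables and adds no times.

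**Blood draws.** Section 12.4.1 gives the sampling as "Serial blood will be collected at: 0 (Baseline), at 0.5, 1, 1.5, and 2 hrs post-Dose 1, immediately prior to Doses" 2 to 7, and then four more after Dose 7. Section 7.1.5 words these last draws as "and at 0.5, 1, 1.5, and 2 hrs post Dose 7".

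**Stated intent.** Section 7.1 says that the time points of both phases "were designed to capture assessments/procedures/blood draws based on comprehensive blood sampling for pharmacokinetic analysis". For the Multiple-Dose Phase, section 7 gives the purpose of sampling: "Blood from a patent line will be collected to assess pharmacokinetics, examine dose proportionality, and estimate effective and safe dosing".

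**Single-Dose Phase, for comparison.** Section 7.1.4 sets "Measurement of vital signs at 15 and 30 minutes and at 1, 1.5, 2, 4, 6, 8, 12, and 24 hours", and the blood draws, respiratory assessments and neurological assessments have the same times. Only pain departs from this: after rescue, "all study procedures (including PK) will continue except collection of pain scores".

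**The concern.** The primary objective, for both phases, is to characterise effectiveness, safety and tolerability; pharmacokinetics is secondary. In the Single-Dose Phase the safety readings follow the blood draws. In the Multiple-Dose Phase they follow them only up to Dose 7. The one dense sampling series after repeated dosing therefore serves the secondary objective alone.

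Section 13.5 summarises vital signs and respiratory and neurological assessments at each time point, and the data monitoring committee reviews individual and aggregate data before each escalation. With the present schedule, the values after Dose 1 are nearly all taken just before the next dose, 4 to 6 h after the last one. Neither the summaries nor the committee would have planned values at 0.5 to 2 h after a repeated dose to compare with those at 0.5 to 2 h after the first.

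**Working it through.** No power or sample-size formula applies. The check is a count of scheduled times, followed by a check of whether the end-of-study visit fills the gap.

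**1. Number of draws (section 12.4.1).** Baseline 1 + post-Dose 1 4 + before Doses 2 to 7 6 + post-Dose 7 4 = 15. This reproduces the maximum of 15 in Table 4, footnote f.

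**2. Pairing with scheduled readings (sections 7.1.5 and 11.1).**

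| Draws | Number | Scheduled reading at that time? |
|---|---|---|
| Baseline | 1 | yes |
| 0.5, 1, 1.5, 2 h after Dose 1 | 4 | yes |
| Before Doses 2 to 7 | 6 | yes |
| 0.5, 1, 1.5, 2 h after Dose 7 | 4 | no |

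Paired: 11 of 15. Unpaired: 4/15 = 27% of all draws, and 4/8 = 50% of the draws at 0.5 to 2 h after a dose. With 36 subjects all reaching Dose 7, that is 36 × 4 = 144 of 36 × 15 = 540 draws; fewer if some leave earlier. In the Single-Dose Phase the draws are baseline plus 10 post-dose times, and all 11 have scheduled vital-sign, respiratory and neurological readings.

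The columns of Table 4 cannot be aligned with certainty in the extracted text, so this count rests on the wording of sections 7.1.5, 11.1 and 12.4.1.

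**3. Doses without a post-dose series.** Dosing is every 4 to 6 h for up to 48 h. On an exact 4 h grid there are 12 doses (last at 44 h); on an exact 6 h grid, 8 (last at 42 h). Scheduled reading times at 0.5 to 2 h: four after Dose 1, none tied to the 7 to 11 later doses.

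**4. Can another scheduled reading fall in the Dose 7 window?** Dose 7 is given at 6 × 4 = 24 h to 6 × 6 = 36 h, so its four draws fall between 24.5 and 38 h. The next scheduled reading is before Dose 8, 4 to 6 h after Dose 7. End of study at 48 h comes 48 − 36 = 12 h to 48 − 24 = 24 h after Dose 7. Neither falls in the window.

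**5. Can end of study fall 0.5 to 2 h after some later dose?** The protocol does not say how intervals will vary within 4 to 6 h, so each row is an assumption. Simulated rows use 400,000 subjects with independent uniform intervals.

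| Intervals | End of study 0.5 to 2 h after the last dose |
|---|---|
| Exact 4, 5 or 6 h (leaves 4, 3 or 6 h) | 0% |
| Uniform 5 to 6 h | about 2% |
| Uniform 4 to 5 h | about 15% |
| Uniform 4 to 6 h (the whole permitted range) | about 28% |
| Uniform 5.5 to 6 h | about 50% |
| Uniform 4 to 4.5 h | about 88% |
| Fixed 4.2 h (48 − 11 × 4.2 = 1.8 h) | 100% |

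In every row it is at most one reading per subject, with no post-dose series around it.

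**The case against.** **Events would still be seen.** A reader might infer that respiratory depression or sedation after Dose 7 could go unnoticed. The documents do not support that. Sections 12.2 and 12.3 require respiratory and CNS monitoring as needed throughout, with respiratory monitoring equipment, and adverse events are documented throughout. Rescue or early termination may also happen to produce a reading in the window. This objection stands in full, and it limits the point to planned values. As-needed monitoring fixes no times, so it cannot give comparable Dose 1 and Dose 7 summaries.

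**No planned analysis needs the pairing.** This also stands. Section 13.6 contains no exposure-response analysis, and section 13.5 does not set readings beside concentrations. The aim of estimating effective and safe dosing is a general purpose, not an analysis plan. Moreover, section 13.6 summarises multiple-dose pharmacokinetics after Doses 1 and 3, whereas the dense sampling follows Doses 1 and 7. It would be wrong to say that a planned concentration-response analysis is undermined.

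**The effectiveness model is unaffected.** AUC_E in section 13.4 can be computed from the scheduled times as they are. Extra pain scores would add only to the by-time-point tables. The case rests mainly on the safety readings.

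**The schedule is consistent.** Sections 7.1.5 and 11.1 agree on the pain times, and sections 7.1.5 and 12.4.1 agree on the post-Dose 7 draws. The statement in section 7.1 about designing times around blood sampling does not promise a reading at every draw. This is a design choice that can be improved, not a contradiction.

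**The gain is limited.** Cohorts have 6 subjects, and only those still on drug at Dose 7 contribute. True, but the extra burden is small as well.

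**Conclusion.** The point holds as a cheap improvement to data recording. In the Multiple-Dose Phase, 4 of 15 planned draws (27%), all at 0.5 to 2 h after Dose 7, have no scheduled vital-sign, oxygen-saturation, respiratory, neurological or pain reading beside them. This is a direct count and needs no assumption. No other scheduled reading falls in that window at any permitted interval. Whether end of study falls 0.5 to 2 h after a later dose does depend on an assumption: about 28% with uniform 4 to 6 h intervals, anywhere from 0% to 100% with others, and one reading at most.

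What is lost is planned, comparable values after repeated dosing for the section 13.5 summaries and the committee's reviews. Event detection, the AUC_E analysis and the planned pharmacokinetic analysis are not lost.

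One neighbouring matter should not be read as support for this point. Section 7.1.6 lists a pharmacokinetic sample at end of study, which would be a 16th for a subject who completes, against the maximum of 15 in Table 4, footnote f. That list serves both phases, and in the Single-Dose Phase the sample can be the scheduled 24 h draw. Footnote f also cites Appendix E, which is not in the text available here and may settle the count.

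**What to change.** 1. In section 7.1.5 and Table 4, record vital signs with oxygen saturation, respiratory assessment and neurological assessment at the four existing post-Dose 7 draws. Summarise them by age group and treatment cohort beside the Dose 1 values.
2. Optionally, record pain at the same times in subjects not yet rescued, for the by-time-point tables only, and amend section 11.1 to match. In that case state in section 13.4 that AUC_E stays on the original times; otherwise subjects unrescued at Dose 7 would be scored on a denser grid than the rest.
3. Reconcile section 13.6, which summarises Doses 1 and 3, with the sampling after Doses 1 and 7.
4. As a separate item, state in sections 7.1.6 and 12.4.1 and in Table 4, footnote f, whether the end-of-study sample counts towards the 15.

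**Cost.** A protocol amendment with IRB approval (section 14.3) at about 20 sites, and eCRF changes. Each subject has four non-invasive assessment sets while an inpatient, at most 36 × 4 = 144 sets in all, with no extra draws, visits or subjects. The burden is nursing time and some disturbed sleep. Subjects who leave before Dose 7 give no values, so the data describe only those still on drug. Any multiple-dose cohort completed before the amendment would have none, which would make comparisons between doses uneven; the documents do not say whether any had been completed. No dose, rescue or stopping rule changes.
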